6.4.1 Migraine Days

A migraine day is defined as any calendar day in which the patient experiences a qualified migraine headache (onset, continuation, or recurrence of the migraine headache). A qualified migraine headache is defined as a migraine with or without aura, lasting for ≥ 30 minutes, and meeting at least one of the following criteria:

1. ≥ 2 of the following pain features:
 - Unilateral
 - Throbbing
 - Moderate to severe
 - Exacerbated with exercise/physical activity
2. ≥ 1 of the following associated symptoms:
 - Nausea and/or vomiting
 - Photophobia and phonophobia

If the patient took a migraine-specific medication (i.e., triptane or ergotamine) during aura, or to treat a headache on a calendar day, then it will be counted as a migraine day regardless of the duration and pain features/associated symptoms.

To further characterize a migraine day, the following information will be collected:

- Date and time of start of headache (i.e., migraine or non-migraine headache)
- Date and time of end of headache
- Worst pain severity per headache
- Pain features (e.g., one-sided, throbbing, worsens with exercise/physical activity)
- Symptoms (e.g., aura, nausea, vomiting, photophobia, phonophobia)
- Use of acute headache medications (medication name (from pre-entered list), date of dosing, number of times taken of each date, number of units taken)

6.4.2 Appropriateness of efficacy assessments

The definition of migraine day (Section 6.4.1) is consistent with the diagnostic criteria of migraine and probable migraine according to the International Classification of Headache Disorder (ICHD-3). The MMD will be calculated using migraine day data collected from the eDiary. Migraine days are commonly used as an endpoint in pivotal trials as acknowledged in the IHS guidelines for controlled trials of drugs in migraine (Tfelt-Hansen 2012).

The mean change in MMD however describes a population-based measure and, given the natural variability in migraine trials, often is associated with small effect sizes. Thus, a clinically important complementary information is the proportion of patients that achieve a certain clinical benefit, which is usually described with achieving at least a 50% reduction of migraine days compared to the individual baseline (“50% responder rate”). In pivotal trials, 50% (or higher) responder rates are usually included as secondary or key secondary outcomes.

Additional PRO scales were included to gather information on functional impact of headache (HIT-6, SF-36).

6.5 Safety

Safety assessments will include:

- Treatment discontinuations due to AEs
- Adverse events (Section 7.1)
- Physical examination
- Vital signs
- ECG
- Height/weight
- Laboratory evaluations
- Pregnancy testing (females of childbearing potential)
- Columbia Suicide Severity Rating Scale (C-SSRS) (Section 7.6)

The timing and frequency of these assessments are outlined in Table 6-1 and Table 6-2.

6.5.1 Physical examination

A complete physical examination will include the examination of general appearance, skin, neck (including thyroid), eyes, ears, nose, throat, lungs, heart, abdomen, back, lymph nodes, extremities, as well as vascular and neurological examination. If indicated based on medical history and/or symptoms, rectal, external genitalia, breast, and pelvic exams will be performed.

A brief physical exam will include the examination of general appearance and will be at all visits starting from Visit 2, except where a complete physical examination is required (see above).

Information for all physical examinations must be included in the source documentation at the study site. Clinically relevant findings that are present prior to randomization must be included in the Medical History part of the eCRF. Significant findings made after first administration of investigational drug, which meet the definition of an Adverse Event must be recorded on the Adverse Event section of the eCRF.

6.5.2 Vital signs

Vital signs include blood pressure, pulse and temperature measurements. After the patient has been sitting for approximately five minutes, with back supported and both feet placed on the floor, systolic and diastolic blood pressure will be measured three times using a validated device, with an appropriately sized cuff. The repeat sitting measurements should be made at approximately 1 – 2 minute intervals and the mean of the three measurements will be used. In case the cuff sizes available are not large enough for the patient's arm circumference, a sphygmomanometer with an appropriately sized cuff may be used. The method to take temperature should be consistent throughout the study.

6.5.3 Height and weight

Height in centimeters (cm) and body weight (to the nearest 0.1 kilogram (kg) in indoor clothing, but without shoes) will be measured.

6.5.4 Laboratory evaluations

A central laboratory will be used for analysis of all specimens collected. Details on the collections, shipment of samples and reporting of results by the central laboratory are provided to investigators in the laboratory manual.

Clinically notable laboratory findings are defined in Appendix 1.

6.5.4.1 Hematology

Hemoglobin, hematocrit, red blood cell count, white blood cell count with differential counts, and platelet count will be measured.

6.5.4.2 Clinical chemistry

Bilirubin (total, direct and indirect), alkaline phosphatase, AST (SGOT), ALT (SGPT), GGT, creatinine and estimated creatinine clearance (GFR) will be measured. Clinical chemistry assessment will be performed at Screening (Visit 0), begin of DBTE (Visit 101), during DBTE two weeks after topiramate titration phase (Visit 108), at the end of DBTE (Visit 199) and at follow up (Visit 201).

6.5.5 Electrocardiogram (ECG)

ECGs must be recorded as outlined in the central ECG reading manual. The preferred sequence of cardiovascular data collection during study visits is ECG collection first, followed by vital signs, and blood sampling. The Fridericia QT correction formula (QTcF) as reported by the central reader should be used for clinical decisions. Single 12 lead ECGs are collected. The original ECGs, printed on non-heat sensitive paper, appropriately signed, must be collected and archived at the study site. Each ECG tracing must be labeled with study number, subject number, date and time, and filed in the study site source documents. For any ECGs with patient safety concerns, two additional ECGs must be performed to confirm the safety finding and forwarded to the central ECG laboratory for assessment. Clinically significant abnormalities must be recorded on the relevant section of the medical history/Current medical conditions/AE eCRFs as appropriate.

6.5.6 Pregnancy and assessments of fertility

All pre-menopausal women who are not surgically sterile will have pregnancy testing. Serum pregnancy tests will be performed at the beginning and end of the study, with urine pregnancy tests performed at the remaining visits. Pregnancy tests during DBTE should be performed/registered by the investigator prior to dosing. The specific schedule is outlined in Table 6-1 and Table 6-2.

6.5.7 Appropriateness of safety measurements

The safety assessments have been selected based upon the safety profile of the drug as reported in the Investigator Brochure and are standard for this patient population and drug class.

6.6 Other assessments

- Headache Impact Test (HIT-6)
- SF-36 V2
- Beck Depression Inventory (BDI)-II

The timing and frequency of these assessments are outlined in Table 6-1 and Table 6-2.

6.6.1 Patient Reported Outcomes (PROs)

Patients will complete all Patient Reported Outcome (PRO) questionnaires using the provided eDiary platform. For those questionnaires that are completed in-clinic, during visits, completion should occur before any other assessments are performed.

All questionnaires will be completed in German, at the scheduled study visit prior to the patient seeing the investigator for any clinical assessment or evaluation. The site staff should check the responses to the questionnaire for completeness and encourage the patient to complete any missing responses.

Patients should be given sufficient space and time to complete all study PROs. If patients experience any difficulties with submission after they complete the PROs, the study staff should assist them with submitting their PRO responses. Attempts should be made to collect responses to all PROs for all patients, including from those who prematurely discontinue prior to the study evaluation completion visit, however, if patients refuse to complete PROs, this should be documented in study source records.

Completed questionnaires will be reviewed and examined by the investigator, before the clinical examination, for responses that may indicate potential adverse events (AEs) or serious adverse events (SAEs). The investigator should review not only the responses to the questions in the questionnaires but also for any unsolicited comments written by the patient. If AEs or SAEs are confirmed, then the physician must record the events as per instructions given in Section 7.1 and Section 7.2 of the protocol.

6.6.1.1 Headache Impact Test (HIT-6)

The HIT-6 is a short-form self-administered questionnaire based on the internet-HIT question pool (Kosinski 2003). The HIT-6 was developed as a global measure of adverse headache impact to assess headache severity in the previous month and change in a patient's clinical status over a short period of time. Six items assess the frequency of pain severity, headaches limiting daily activity (household, work, school, and social), wanting to lie down when headache is experienced, feeling too tired to work or do daily activities because of headache, feeling "fed up" or irritated because of headache, and headaches limiting ability to concentrate

or work on daily activities. Each of the 6 questions is responded to using 1 of 5 response categories: “never,” “rarely,” “sometimes,” “very often,” or “always.”

For each HIT-6 item, 6, 8, 10, 11, or 13 points, respectively, are assigned to the response provided. These points are summed to produce a total HIT-6 score that ranges from 36 to 78. HIT-6 scores are categorized into 4 grades, representing little or no impact (49 or less), some impact (50 – 55), substantial impact (56 – 59), and severe impact (60 – 78) due to headache.

No recall period is specified for the first 3 items. The recall period is the past 4 weeks for the last 3 items. Patients will complete this in their eDiary during their scheduled clinic visit, at the frequency outlined in Table 6-1 and Table 6-2.

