5.6.2 Discontinuation of study treatment

Discontinuation of study treatment for a patient occurs when study drug is stopped earlier than the protocol planned duration, and can be initiated by either the patient or the investigator.

The investigator must discontinue study treatment for a given patient if, on balance, he/she believes that continuation would negatively impact the risk/benefit of trial participation.

Study treatment must be discontinued under the following circumstances:

- Patient wish
- Pregnancy (see Section 6.5.6 and Section 7.5)
- Use of prohibited treatment as per recommendations in Table 5-1
- Any situation in which study treatment might result in a safety risk to the patient
- Any laboratory abnormalities that in the judgment of the investigator, taking into consideration the patient's overall status, prevents the patient from continuing participation in the study

If discontinuation of study treatment occurs, the patient should NOT be considered withdrawn from the study, and should continue recording in the eDiary as per protocol. Also, patients who discontinued treatment from the double-blind treatment epoch will follow the abbreviated visit schedule until the follow up visit (week 28) is reached (Table 6-2). These visits should be performed with all assessments outlined in Table 6-2. At a minimum, the following data should be collected at clinic visits or via telephone visits:

- new/concomitant treatments
- adverse events / serious adverse events

If the patient cannot or is unwilling to attend any visit(s), the site staff should maintain regular telephone contact with the patient, or with a person pre-designated by the patient. This telephone contact should preferably be done according to the study visit schedule.

Patients who prematurely discontinue the study for any reason should be scheduled for a visit as soon as possible, at which time all of the assessments listed for the final visit (Visit 199) will be performed. At this final visit, the adverse event and concomitant medications should be reconciled on the eCRF. Patients will return for a follow-up visit approximately 8 weeks after their last dose of study medication, and perform the study procedures outlined in Table 6-1.

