- 3 – Including prior prophylactic medication.
- 4 – Includes blood pressure, pulse and temperature.
- 5 – Patient brings to each visit for use at site
- 6 – To be completed during applicable study visits before study drug administration, where applicable.
- 7 – Should also be performed at unscheduled visits.
- 8 – SAEs will be collected after signing of the informed consent through the end of the Follow-Up Epoch (8 weeks after the last IMP injection). Non-serious AEs will be collected after randomization (Visit 101) through the end of the Follow-Up Epoch (8 weeks after the last IMP injection).
- 9 – Study drug is administered by study staff, during the applicable study visits, q.m., s.c..
- 10 – Oral study drug will be dispensed to the patient at the center during the applicable study visit for home application.
- 11 – Sites will access the Interactive Response Technology (IRT) System to register study early termination.
- 12 – Should be additionally performed at any visit if deemed necessary by the investigator due to AEs.
- 13 – Should be performed/registered by the investigator prior to dosing during DBTE.
- TD = Treatment discontinuation; PFS = Prefilled syringe; PSD = Premature subject discontinuation; X = Assessment to be recorded in the source documents and the clinical data base; S = Assessment to be recorded as source documentation only.

Table 6-2 Abbreviated schedule of assessments (ASA) for patients with Treatment Discontinuation (TD)

Visit number	V105-ASA	V108-ASA	V109-ASA	V110-ASA	V111-ASA	V199-ASA	V201-ASA ²
End of Week¹	4	8	12	16	20	24	28
Complete Physical Exam						S	
Brief Physical Exam	S	S	S	S	S		
Weight						X	X
Vital Signs ³	X	X	X	X	X	X	X
Chemistry/Hematology ¹²		X				X	X
Serum Pregnancy						X	
Urine pregnancy	S	S	S	S	S		X
ECG						X	
Clinical Outcomes (eDiary)	eDiary should be maintained						
SF-36 ⁴ (eDiary)	X	X	X	X	X	X	
HIT-6 ⁴ (eDiary)	X	X	X	X	X	X	
C-SSRS	X	X	X	X	X	X	
Concomitant Medications	X	X	X	X	X	X	X
Adverse Events ⁵	X	X	X	X	X	X	X
Serious Adverse Events ⁵	X	X	X	X	X	X	X
Follow Up Phase Completion form							X

1 – All study visit target dates are to be calculated from the Day 1 visit date, and all study procedures for a given visit should be completed in the same day.

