**2.1.1.2 Visit and analysis window**

Since the actual visit for a subject may not exactly coincide with their targeted visit date, the actual visit date is mapped to a study visit.

The nearest study day window will be utilized to define study visit for lab, vital signs, ECG, C-SSRS and some PROs collected during office visits (HIT-6, SF-36v2, ██████████) before dose is administered.

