### **2.7.3 Handling of missing values/censoring/discontinuations**

For the exploratory endpoints “Proportion of patients achieving at least a 5 points reduction from baseline in HIT-6 total score” and “Proportion of patients achieving at least 5 points increase from baseline to week 24 in PCS and MCS (SF-36v2)” missing response data will be imputed as non-response (non-responder imputation).

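### Patients who stop drug and miss the Week 24 visit have no written home route for HIT-6 and SF-36, and the SAP gives two conflicting rules for the missing score

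*Protocol*

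**What the plan says.** **Where the questionnaires are completed.** Protocol 6.6.1.1 on HIT-6: "Patients will complete this in their eDiary during their scheduled clinic visit". SAP 2.1.1.4 repeats this. Protocol 6.6.1 covers every questionnaire: "All questionnaires will be completed in German, at the scheduled study visit", before the patient sees the investigator. SAP 2.1.1.2 lists HIT-6 and SF-36 among "some PROs collected during office visits".

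**What happens after stopping drug.** Under Protocol 5.6.2 the patient stays in the study and "should continue recording in the eDiary as per protocol". Abbreviated visits are to include everything in Table 6-2, which marks HIT-6 and SF-36 at each visit through V199-ASA (Week 24). Protocol 6.6.1 also asks sites to try to obtain questionnaires from all patients, including those who discontinue early.

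**The fallback.** Protocol 5.6.2 continues: "If the patient cannot or is unwilling to attend any visit(s), the site staff should maintain regular telephone contact with the patient". The minimum data set for a clinic or telephone visit is new and concomitant treatments plus AEs and SAEs.

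**Missing scores.** For the HIT-6 and SF-36 responder endpoints, SAP 2.7.3 provides that "missing response data will be imputed as non-response (non-responder imputation"; the table in SAP 2.7.2 agrees. SAP 5.1 says that missing exploratory endpoints are not imputed.

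**The concern.** A patient who has stopped drug and is reached only by telephone at Week 24 can still supply migraine days, because these come from daily eDiary entries. HIT-6 and SF-36 run on the same eDiary platform, but the plan describes their completion only at a visit. The score may then be missing for a logistic reason, in a group defined by stopping treatment.

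AE-related stopping is the primary endpoint, and the trial is designed to show that it differs between arms. Protocol 3.2 calls discontinuation rates for approved migraine treatments high. Protocol 3.6 describes AE discontinuations on erenumab as similar to placebo. Protocol 5.5.4 requires patients who cannot tolerate 50 mg topiramate to stop drug but stay in the trial. Missing scores could therefore be more frequent on topiramate.

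At stake is the comparison on the HIT-6 and SF-36 responder endpoints. They are exploratory, but Protocol 1.2 says the data will support health technology assessment and reimbursement.

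**Working it through.** The plan states no figure on this point, so there is none to reproduce. What follows is an illustration.

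**Inputs**
- From the documents: 375 patients per arm (SAP 1.1); 1:1 allocation (Protocol 5.2); two-sided 5% level (stated in Protocol 9.3.2 for the primary test, borrowed here).
- Assumed, with no figure in the documents:
  - stop rate on erenumab sE = 10% and on topiramate sT = 25% to 35%;
  - share of stoppers without a Week 24 score q = 25% to 50%, equal in both arms;
  - true response among those patients rs = 25% to 40%;
  - the same overall true response r in both arms, 40% unless stated otherwise.

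**Rule A: missing counts as non-response (SAP 2.7.2 and 2.7.3).** The observed rate in an arm is r − s × q × rs, so the shift in the risk difference toward erenumab is q × rs × (sT − sE).
- Low end: 0.25 × 0.25 × (0.25 − 0.10) = 0.0094, or 0.9 points.
- Middle: 0.375 × 0.325 × (0.30 − 0.10) = 0.0244, or 2.4 points.
- High end: 0.50 × 0.40 × (0.35 − 0.10) = 0.050, or 5.0 points.
- No scores lost (q = 0), or equal stop rates: zero.

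A two-proportion z test with 375 per arm and r = 40% would reject a true null in about 6% of trials at the low end and 30% at the high end. For r between 30% and 60%, the high end runs from 28% to 35%.

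The result depends heavily on the assumed ranges. With stop rates of 20% to 40% against 10%, q of 25% to 100% and rs of 20% to 40%, the shift runs from 0.10 × 0.25 × 0.20 = 0.5 points to 0.30 × 1.00 × 0.40 = 12 points. The top of that range needs every stopper to be unscored.

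**Rule B: missing is not imputed, so the patient drops out (SAP 5.1).** The observed rate becomes (r − s × q × rs) / (1 − s × q). Take sT = 35%, sE = 10%, q = 50%, r = 40%.
- rs = 25%: topiramate (0.40 − 0.04375) / 0.825 = 43.2%; erenumab (0.40 − 0.0125) / 0.95 = 40.8%. The shift is 2.4 points toward topiramate.
- rs = 40%, equal to r: both arms stay at 40% and there is no shift.

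Under the same inputs with rs = 25%, Rule A gives 0.50 × 0.25 × 0.25 = 3.1 points toward erenumab. The choice between the two SAP rules can therefore change the direction of the distortion as well as its size.

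**The case against.** The plan already gives sites most of what they need. Full abbreviated visits with both questionnaires are the default, the telephone list is a floor, and Protocol 6.6.1 asks for attempts in patients who discontinue. SAP Table 2.1.1.2-1 accepts Week 24 data from Day 155 to Day 182, so a rescheduled visit counts. Protocol 6.6.1 speaks of a study visit rather than a clinic visit, and its reference to questionnaires completed in-clinic suggests that some may not be. The SF-36 section has no clinic-visit sentence of its own. Nothing forbids completion at home. All of this stands, and it confines the point to patients who do not attend at Week 24. For them, the request to try comes with no method.

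A reader might infer more than the documents support:
- *That stoppers lose their Week 24 score.* This is a risk for non-attenders, not a rule for stoppers.
- *That the eDiary stays at home.* Table 6-1 footnote 5 reads "Patient brings to each visit for use at site". Its row is not shown, but the wording fits the device. What the documents support is use at home between visits.
- *That these patients certainly count as non-responders.* SAP 5.1 says otherwise.
- *That more stops must mean more lost scores on topiramate.* This needs a similar lost share per stopper in both arms, for which the documents give no figure.
- *That COVID-19 adds to the imbalance.* SAP 2.3.1 only tabulates related deviations, and nothing suggests that they differ by arm.

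It is also fair to say that no confirmatory claim rests on these endpoints, so the rejection rates above only show scale.

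**Conclusion.** The gap is real but narrow. The plan ties HIT-6 and SF-36 to the visit, omits them from the telephone minimum, and writes no home route for patients who still use the eDiary. The SAP then has two incompatible rules for the missing responder status, and either can distort the comparison if stopping differs by arm.

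The documents do not allow the size to be derived. The 0.9 to 5.0 points toward erenumab hold only under non-responder imputation and the assumed stop, loss and response rates, with equal loss per stopper in both arms. They should not be read as an estimate of bias in this trial.

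The primary endpoint and the secondary migraine-day endpoint are not affected. The MMRM footnote in SAP 2.7.2 points to other, partly redacted exploratory analyses that would not use non-responder imputation. Priority: optional to low.

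**What to change.** 1. In Protocol 6.6.1 and 6.6.1.1 and SAP 2.1.1.4, state that when a visit is missed or held by telephone, HIT-6 and SF-36 are completed on the patient's eDiary at home within the visit window. Keep clinic completion for patients who attend.
2. Add both questionnaires to the minimum data set in Protocol 5.6.2.
3. Reconcile SAP 5.1 with SAP 2.7.2 and 2.7.3, so that one rule governs missing HIT-6 and SF-36 responder status.
4. Report missing Week 24 scores by arm and treatment status, with one sensitivity analysis to the chosen rule.

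The cost is protocol and SAP wording, an eDiary setting and a small amount of extra output, with no extra visits. The downside is some unsupervised completion, although HIT-6 is described as self-administered. Patients unwilling to attend may also decline at home, so not every score will be recovered.
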